8.1.2 Measures taken to minimize or avoid bias

The study will be conducted according to BIOTRONIK's internal Standard Operating Procedures to minimize and avoid potential bias.

The study does not require randomization or blinding as it does not require a control group.

It will be conducted at up to 10 sites to avoid a hospital-specific bias caused by the specific hospital environment or the programmer user. A maximum number of 30 programmer use cases (implantations and FUs) per site is defined to avoid site specific bias in case of high enrollment rates of single sites. Exemptions will be communicated in written form in case enrollment is too slow.

Furthermore, the number of implantations and follow-ups for a specific implant type is defined for the whole study to avoid an unbalanced usage of specific, implant related programmer functions. The 50 implantation and 100 follow-up (including PHD) cases should be distributed as follows:

- IPG, ICD: ~15 implantations and ~20 follow-up cases for each
- ICM: ~20 follow-up cases
- CRT-D /-P: ~20 implantations and ~40 follow-up cases for both combined

As no PSA measurements will be performed for ICMs no implantation cases or PHDs shall be performed for ICMs, but only follow-up cases.

A survey for implantation and follow-up numbers for each implant type is implemented in the iMedNet system. The sponsor will immediately inform all sites whenever the required number of a certain implant type has been reached.

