11.2 Sample size

No hypotheses can be pre-specified for this clinical investigation, which is completely exploratory.

This clinical investigation should be able to identify unforeseen safety problems. While it is unlikely that the number of ADEs or DDs will be sufficient for inferential statistical conclusions, a discussion of the types of events and of the circumstances of their appearance might reveal indicators for hidden risks and trigger further dedicated investigations or statistical tests to substantiate such findings.

Unforeseen safety problems are more likely related to software problems between Renamic Neo and implanted devices but less likely to hardware problems of the Renamic Neo. Thus, the sample size is related to use cases per implantation, pre-hospital discharge, and follow-up but not to the total number of Renamic Neo devices.

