11.9 Specification of subgroups

Potential critical events will be analyzed whether there is any connection to the subgroups IPG, ICD, CRT, or ICM.

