### **1.2. General information**

The text contains verbatim excerpts from the CIP. Such excerpts are italicized with grey background; e.g.

....

The main aspects and the design of the clinical investigation are presented in chapters 1-4.

General statistical procedures are summarized in chapter 5. Those methods are used in case there is no other specification within this document.

Definitions of the specific dates, e.g. enrollment and termination are presented in chapter 6.

Specific analysis sets are defined in chapter 7.

Descriptive and inferential statistical analyses are handled in following chapters.

Thereby the following statistical considerations are specified:

- Definition of the analysis set for the following analyses, e.g. excluding patients without any measured or imputed data for this endpoint.
- Definition of the endpoint(s) to be analyzed including references to the source data, e.g. CRF sheet and item.
- Treatment of missing and spurious data for evaluation of the above endpoint(s).
- Exclusion of particular information from the evaluation of the above endpoint(s) in addition to the exclusion of patients from the analysis set.
- Descriptive analyses including tables and figures
- Statistical alternative hypothesis/hypotheses (HA) to analyze the above endpoint(s) if available.
- Statistical tests intended to analyze the above hypothesis/hypotheses if available.

All variables are defined in tables using the following columns:

- **Data file** Name of a data file exported from the CDMS with one data row per unique identifier (e.g. patient-specific "patient display ID full" or event-specific record ID); additionally, a new data file ("data SAR") might be generated by merging all relevant data from the original CDMS data files and generating derived variables (e.g. BMI from weight and height or date of first AE episode)
- **Notes** Information whether data has to be presented with "descriptive" methods as defined in the following sub-chapter, data for "case listings" of original data for each patient specified, or "no report" for data needed for generating of derived variables only
- **Variable name** Original name of a variable in the CDMS data file or name of a derived variables (indicated with a suffix " SAR");
- **Variable label** Original labels from the CDMS data will be used for generating the SAR unless a new label is defined in this document ("NEW"); labels might be omitted or shortened ("...") if remaining clear

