 IF analysis set enr SAR = Yes AND  
 any general assessments per patient with  
 ([PRSVPRG = Yes AND autom SVTYP = Pre-hospital discharge follow-up (PHD)] OR  
 [PRSVPRG = Yes AND autom SVTYP = Regular follow-up after PHD])  
 THEN analysis set FUP SAR = Yes  
 ELSE analysis set FUP SAR = No

Subgroups

Data file, identifier patient display id full & DIDVTYP	Variable name	Variable label	Variable level	Nominal values
device log details	helpvar device type	hidden technical field: Short name for General type of device	nominal	
 
○ CRT
 
○ CRT-P
 
○ ICD
 
○ ICM
 
○ IPG
 

Data file, identifier patient display id full	Variable name	Variable label	Variable level	Nominal values
data SAR	subgroup device type SAR 	Subgroup type of device	nominal	
 
○ CRT
 
○ CRT-P
 
○ ICD
 
○ ICM
 
○ IPG
 

 Patient-specific type of device data for helpvar device type not missing  
subgroup device type SAR = helpvar device type

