### 10.2. Variables

#### Adjudicated Adverse Device Effects / Device Deficiencies

Data file, identifier record id	Notes	Variable name	Variable label	Variable Level	Nominal values
internal adjudication	Case listing for AETYP = AE	AETYP	Type of event	nominal	o AE o DD
		AESTDT	Onset date	date	n.a.
		PRUCASE	Related use case	nominal	o Implementation o PHD / Follow-up
		DEIDV	Related investigational device	nominal	o Renamic Neo programmer o ECG cable PK-222-L
		DIPRGSNR	Programmer serial number	text	n.a.
		DIECBID	ESG cable ID	nominal	01, 02, ..., 25
		AERELIDV	Adverse Event is related to the investigational device (device related ADE)	nominal	o Not related o Unlikely o Possible o Probable o Causal relationship
		AESER	Adverse Event is serious	nominal	o Yes o No
		AERELSET	Adverse Event is relevant for ADE/DD endpoint	nominal	o Yes o No
CORELSET	Please specify reason for No	text	n.a.		

 analysis set imp SAR = Yes and PRUCASE = Implementation

Data file, identifier record id	Notes	Variable name	Variable label	Variable Level	Nominal values
internal adjudication	Case listing for AETYP = DD	AETYP	Type of event	nominal	o AE o DD
		DERCDT	Date of detection	date	n.a.
		PRUCASE	Related use case	nominal	o Implementation o PHD / Follow-up
		DEIDV	Related investigational device	nominal	o Renamic Neo programmer o ECG cable PK-222-L
		DIPRGSNR	Programmer serial number	text	n.a.
		DIECBID	ESG cable ID	nominal	01, 02, ..., 25
		DEADED	Device efficiency is relevant for ADE/DD endpoint	nominal	o Yes o No
		COADED	Please specify reason for No	text	n.a.

Data file, identifier patient display id full	Notes	Variable name	Variable label	Variable Level	Nominal values
data SAR	descriptive	any ade SAR 	Any Adverse Device Effect (serious or non-serious) based on internal adjudication	nominal	o Yes o No
data SAR	descriptive	any sade SAR 	Any Serious Adverse Device Effect based on internal adjudication	nominal	o Yes o No
data SAR	descriptive	any dd SAR 	Any Device Deficiency	nominal	o Yes o No
data SAR	descriptive	any ade dd SAR 	Any Adverse Device Effect (serious or non-serious) or Device Deficiency based on internal adjudication	nominal	o Yes o No
data SAR	descriptive	n ade SAR 	Number of Adverse Device Effects (serious or non-serious) based on internal adjudication	metric to be reported as nominal	o 1 o 2 ...

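### Protocol 11.9 and SAP 5.6 commit to examining events by implant type, but SAP chapters 10 and 11 specify no ADE or DD table or listing that does so

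*SAP*

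**What the plan says.** Protocol 11.9 states: "Potential critical events will be analyzed whether there is any connection to the subgroups IPG, ICD, CRT, or ICM". SAP 5.6 repeats this without adding a variable, table or listing.

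Protocol 8.1.2 plans cases by implant type: "IPG, ICD: ~15 implantations and ~20 follow-up cases for each"; "ICM: ~20 follow-up cases"; and "CRT-D /-P: ~20 implantations and ~40 follow-up cases for both combined". CRT is thus one group both in the subgroup commitment and in the planned case mix.

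Protocol 11.2 says where surprises are expected: "Unforeseen safety problems are more likely related to software problems between Renamic Neo and implanted devices". It adds that there will probably be too few events for inference, so the kinds of event and the conditions under which they arose will be discussed.

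SAP 7, footnote 5, derives the subgroup variable by copying a short name from the device log: "subgroup device type SAR = helpvar device type". The levels listed are CRT, CRT-P, ICD, ICM and IPG.

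SAP 10 specifies the implantation endpoint outputs: one listing headed "Case listing for AETYP = AE", a matching one for DDs, and eight patient-level variables marked as descriptive. SAP 11 repeats chapter 10 for pre-hospital discharge (PHD) and follow-up cases.

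**The concern.** The study has no hypothesis and no pass/fail criterion. Its safety result is therefore the endpoint tables, the listings and the discussion built on them. The protocol regards the interface between programmer and implant as the likelier source of an unforeseen problem, so the type of implant is one of the first things a reader will want to know about any event. A problem confined to one implant type would appear in the pooled table as a low overall frequency, and the listing beside it would not show which implant was involved.

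The unmatched levels add a smaller risk. Once the variable is used, a row labelled CRT would leave out the CRT-P patients and so would not be the CRT group that the protocol names.

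**Working it through.** No figure in the plan depends on this point, so the check is mainly a trace of the subgroup variable through the SAP, followed by the planned denominators.

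**1. The plan's own numbers.** The planned cases by type add up: 15 + 15 + 20 = 50 implantations and 20 + 20 + 20 + 40 = 100 follow-up cases. The detection figures in Protocol 11.2.1 and 11.2.2 are binomial tails at a 5% event probability; for at least one event the formula is 1 − 0.95^n. For at least one, two and three events:

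- n = 50: 92.31%, 72.06%, 45.95% (stated: 92, 72, 46).
- n = 100: 99.41%, 96.29%, 88.17% (stated: 99, 96, 88).

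All six reproduce.

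**2. Where implant type appears in the SAP.**

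| SAP place | What it specifies | Implant type |
|---|---|---|
| 5.1 | Dummy shells with and without grouping | Shown as an example; not said which outputs use it |
| 5.6 | Repeats Protocol 11.9 | Four groups named; no output attached |
| 7, footnote 5 | Derives the subgroup variable | Five levels; not referenced again |
| 10.1, footnote 15 | Selects by analysis set and use case | None |
| 10.2, listings | Event type, date, use case, investigational device, programmer serial number, cable ID, adjudication items | None |
| 10.2, footnotes 16–23 | Any and number of ADE, SADE, DD, and ADE or DD | None |
| 10.5 | Refers to 5.1 | Does not choose a shell |
| 11.1, footnote 24 | Repeats chapter 10 | None |
| 15.1 and 16.1 | Tabulate device and lead models | Not crossed with events |

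**3. Matching the levels to the protocol.**

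| Protocol group | SAP level(s) | Planned implantations | Planned follow-up cases (incl. PHD) |
|---|---|---|---|
| IPG | IPG | about 15 | about 20 |
| ICD | ICD | about 15 | about 20 |
| CRT | CRT and CRT-P | about 20 | about 40 |
| ICM | ICM | none | about 20 |

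Only CRT fails to match. Reading the SAP level CRT as CRT-D is an inference from the device types in SAP 15.1. The documents give no planned split between CRT-D and CRT-P.

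**4. What pooling hides, as an illustration.** Assume the planned numbers are met exactly and two ICD implantation patients each have one DD, with no other events. The specified table gives 2/50 = 4.0%. By implant type it would be 0/15 for IPG, 2/15 = 13.3% for ICD and 0/20 for CRT. The events are the same and none is lost; only their distribution is hidden.

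**The case against.** The best defence is that this is a gap in specification and not a dropped analysis. SAP 5.6 keeps the commitment. SAP 1.2 says of the chapter 5 procedures: "Those methods are used in case there is no other specification within this document". SAP 5.1 has shells grouped by type of implanted device, and SAP 10.5 refers to 5.1. This largely stands: a reader might infer that the implant-type analysis has been abandoned, and the documents do not support that. What remains is that 5.1 offers both kinds of shell without saying which outputs get which. Two analysts could follow the SAP faithfully and differ on whether any table by implant type exists.

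A reader might also infer that events could not be traced to an implant. That is not so. The subgroup variable and the endpoint flags sit in the same patient-level dataset, and the device log holds type and model per patient. Likewise, the two CRT levels can be added together without loss.

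The promise concerns potential critical events, a term that neither document defines. Reading it as ADEs and DDs is an inference, supported by Protocol 7.2.2 and 11.5. Discussing a handful of events one by one, implant type included, could arguably satisfy it. That is fair, but such a discussion would still need implant type in the listing.

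Finally, one might set per-type detection probabilities (53.7% at n = 15, 64.2% at n = 20, 87.1% at n = 40, each at a 5% rate) against the stated 92% and 99% and call the latter misleading. They are not. They are conditional on a 5% probability in the population, and a 5% problem confined to ICD implantations is only 5% × 15/50 = 1.5% in the planned mix. The per-type figures reflect sample size and would be the same with or without subgroup tables. Nor do the quotas show that the protocol planned for a power comparison by type: Protocol 8.1.2 sets them to keep the use of implant-specific functions balanced.

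**Conclusion.** The point holds as under-specification. The commitment stands in Protocol 11.9 and SAP 5.6 and the variable has been derived, but chapters 10 and 11 never call it. Followed literally, they give pooled counts and listings without implant type. The mismatch between five levels and four groups is real but is cured by a one-line recode.

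The size is modest. The study is exploratory, few events are expected, and groups of about 15 to 20 implantations and 20 to 40 follow-up cases allow description only. The consequence is a less informative safety table and listing, not a wrong estimate. The conclusion assumes that potential critical events include ADEs and DDs; the group sizes assume that the planned case mix is roughly achieved.

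**What to change.** Three changes to the SAP:

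- **Footnote 5:** recode CRT and CRT-P to a single CRT level, so that the variable has the protocol's four groups.
- **10.5 and 11:** state that the ADE, SADE, DD, and ADE-or-DD variables are tabulated overall and by this variable, with the denominator for each group and no tests. The implantation table will have three groups, since ICM patients enter for follow-up only.
- **10.2 listings:** add implant type and model to both the AE and the DD listing, merged by patient ID. Take the model directly from the device log, or first correct footnote 29 in SAP 15.1. That footnote joins pacemaker and ICD with AND, which no single device record can satisfy.

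The cost is a few lines of wording and some extra rows and columns from data already collected. Protocol 11.8 allows the SAP to be updated before database freeze or closure. If closure has passed, the tables can be added and reported as a deviation from the SAP. Protocol 11.2 needs no change.

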## 8. Data for a CONSORT diagram and “study realization”

### 8.1. Analysis set

Unless otherwise specified, all analyses are performed for the enrollment analysis set.

### 8.2. Enrollment

- Date of FPI
- Date of LPI
- Number of patients
- Number of patients per site

#### Inclusion criteria

Data file, identifier patient display id full	Notes	Variable name	Variable label	Variable level	Nominal values
enrollment	descriptive	TIINC01	Patient is planned for de novo implantation or already has a BIOTRONIK active, implantable device	nominal	 Yes  No
		TIINC02	Patient is able to understand the nature of the study and provides written informed consent	nominal	 Yes  No
		TIINC01 type	Type of inclusion criterion	nominal	 Patient is planned for de novo implantation  Patient has already an implanted device

#### Exclusion criteria

Data file, identifier patient display id full	Notes	Variable name	Variable label	Variable level	Nominal values
enrollment	descriptive	TIEXC01	Patient is implanted with a Stratos pacemaker	nominal	 Yes  No
		TIEXC02	Patient is pregnant or breastfeeding	nominal	 Yes  No
		TIEXC03	Patient is less than 18 years old	nominal	 Yes  No
		TIEXC04	Patient is planned for implant exchange or upgrade	nominal	 Yes  No

 analysis set enr SAR = Yes

### 8.3. Termination

- Date of FPO
- Date of LPO

Data file: Identifier patient display id full	Notes	Variable name	Variable label	Variable level	Nominal values
termination	descriptive	DSRTRM	Regular study termination	nominal	o Yes o No
termination	Descriptive for DSRTRM = No	DSETRREA	Reason for early study termination	nominal	o Patient moved away from investigational center o Patient is lost to follow-up o Patient withdrew consent to study participation o Patient death o Drop-out according to protocol o Enrollment failure

Data file: Identifier patient display id full	Notes	Variable name	Variable label	Variable level	Nominal values
enrollment	Case case listing for DSETRREA =	DMICDT i	Patient: Date of informed consent signature	date	n.a.
termination	Drop-out according to protocol	DSTRDT i	Date of study termination	date	n.a.
		DSDRPPRO	Reason for early study termination	nominal	o No implantation of an active implantable BIOTRONIK device o Other
		CODRPPRO	Please specify Drop-out according to protocol - Other	text	...

### 8.4. Fu duration

The FU duration has to be analyzed separately for the implantation and follow-up analysis set.

Data file: Identifier patient display id full	Notes	Variable name	Variable label	Variable level	Nominal values
data SAR	descriptive and cumulative sum		FU duration SAR 	scale	n.a

 analysis set imp SAR = Yes

 analysis set FUP SAR = Yes

 FU duration SAR = DSTRDT - DMICDT

## 8.5. Investigations

The following frequency has to be analyzed for the implantation analysis set .

Data file: Identifier patient display id full	Notes	Variable name	Variable label	Variable level	Nominal values
data SAR	descriptive	PHD renamicneo SAR 	PHD with Renamic Neo	nominal	 Yes  No

The following frequencies have to be analyzed for the PHD/FUP analysis set

Data file: Identifier patient display id full	Notes	Variable name	Variable label	Variable level	Nominal values
data SAR	descriptive	PHD renamicneo SAR	PHD with Renamic Neo	nominal	 Yes  No
data SAR	descriptive	FU renamicneo SAR 	Fu with Renamic Neo	nominal	 Yes  No

 analysis set imp SAR = Yes

 If any general assessments per patient with  
(PRSVPRG = Yes AND autom SVTYP per patient = Pre-hospital discharge follow-up (PHD))  
THEN PHD renamicneo SAR = Yes  
ELSE PHD renamicneo SAR = No

 analysis set PHD FUP SAR = Yes

 If any general assessments per patient with  
(PRSVPRG = Yes AND autom SVTYP per patient = Regular follow-up after PHD)  
THEN PHD renamicneo SAR = Yes  
ELSE PHD renamicneo SAR = No

## 9. Baseline

CIP chapter 11.12 chapter 7.5 Further data of interest

General information

- Patient demographics and medical history

### 9.1. Analysis set

All analyses are performed for enrollment analysis set.

### 9.2. Variables

#### Baseline / Demographic data

Data file, identifier patient display id full	Notes	Variable name	Variable label	Variable level	Nominal values
baseline	descriptive	DMSEX	Gender	nominal	o Male o Female
	descriptive	DMAGE	Age [Years]	scale	n.a.
baseline	descriptive	VSHGHT	Height [cm]	scale	n.a.
	descriptive	VSWGHT	Weight [kg]	scale	n.a.
	descriptive	VSBMI	BMI [kg/m2]	scale	n.a.

#### Medical history / Heart Failure

Data file, identifier patient display id full	Notes	Variable name	Variable label	Variable level	Nominal values
medical history	descriptive	MHHF	History of Heart failure	scale	o Yes o No
	descriptive for MHHF = Yes	CVNYHA	Current NYHA classification	to be reported as nominal variable	o 1 o 2 o 3 o 4

#### Medical history / Coronary Artery Disease

Data file, identifier patient display id full	Notes	Variable name	Variable label	Variable level	Nominal values
medical history	descriptive	MHCAD	History of coronary artery disease	nominal	o Yes o No
	Descriptive for MHCAD=Yes	MHMI	Prior myocardial infarction	nominal	o Yes o No
		PRRVC	Prior revascularization (PCI or CABG)	nominal	o Yes o No

 analysis set enr SAR = Yes

Medical history / Brady- and Tachyarrhythmias

Data file, identifier patient display id full	Notes	Variable name	Variable label	Variable level	Nominal values
medical history	descriptive	MHSSS	History of sick sinus syndrome	nominal	 Yes  No
	descriptive	MHAVB	History of AV block	nominal	 Yes  No
	descriptive for MHAVB = Yes	MHAVBTYP	Type of AV block	to be reported as nominal variable	 1  2  3
	descriptive	MHBBB	History of bundle branch block	nominal	 Yes  No
	descriptive	MHAFB	History of atrial fibrillation	nominal	 Yes  No
	descriptive for MHAFB = Yes	CVAFBTYP	Type of atrial fibrillation	nominal	 Paroxysmal  Persistent  Long-standing persistent  Permanent
	descriptive	MHAVA	History of other atrial/supraventricular arrhythmias	nominal	 Yes  No
	descriptive	MHVA	History of ventricular arrhythmias	nominal	 Yes  No

Data file, identifier patient display id full	Notes	Variable name	Variable label	Variable level	Nominal values
medical history	case listing for MHAVA = Yes	COAVA	Specification of other type of atrial/supraventricular tachycardia	text	...
	case listing for MHVA = Yes	COAV	Specification of ventricular arrhythmias	text	...

Medical history / known comorbidities

Data file, identifier patient display id full	Notes	Variable name	Variable label	Variable level	Nominal values
medical history	descriptive	MHHP	Hypertension (including well-controlled)	nominal	 Yes  No
	descriptive	MHVHD	Valvular heart disease	nominal	 Yes  No
	descriptive	MHCVD	History of cerebrovascular disease (e.g. TIA / Stroke)	nominal	 Yes  No
	descriptive	MHPVAD	Peripheral vascular/arterial disease	nominal	 Yes  No
	descriptive	MHASTH	Asthma or other chronic lung disease (except COPD)	nominal	 Yes  No
	descriptive	MHCOPD	Chronic obstructive pulmonary disease (COPD)	nominal	 Yes  No
	descriptive	MHSAP	Sleep apnoea	nominal	 Yes  No
	descriptive	MHLIVR	Chronic liver disease	nominal	 Yes  No
	descriptive	MHDIAM	Diabetes mellitus	nominal	 Yes  No
	descriptive	MHANEM	Anemia	nominal	 Yes  No
	descriptive	MHCNCR	Cancer	nominal	 Yes  No
	descriptive	MHHPLP	Hyperlipidemia	nominal	 Yes  No
	descriptive	MHCMBOTH	Other comorbidities	nominal	 Yes  No

Data file, identifier patient display id full	Notes	Variable name	Variable label	Variable level	Nominal values
medical history	case case listing for MHVHD = Yes	COVHD	Further specification of valvular heart disease (e.g. type, severity)	text	n.a.
	case listing for MHCMBOTH = Yes	COCMBOTH	Specification of other comorbidities	text	n.a.

